Appendix 2. ECOG Status Scores

Status	Eastern Cooperative Oncology Group (ECOG) Performance Status**
0	Fully active, able to carry on all predisease performance without restriction.
1	Restricted in physically strenuous activity but ambulatory and able to carry out work of a light or sedentary nature, eg, light housework, office work.
2	Ambulatory and capable of all self-care, but unable to carry out any work activities. Up and about more than 50% of waking hours.
3	Capable of only limited self-care, confined to bed or chair more than 50% of waking hours.
4	Completely disabled. Cannot carry on any self-care. Totally confined to bed or chair.
5	Dead.

Available at: http://www.ecog.org/general/perf_stat.html. Accessed January 4, 2008.

Appendix 3. Inhibitors and Inducers of CYP3A

Inhibitors and inducers of CYP3A are defined as follows. A comprehensive list of inhibitors can be found at the following website: <http://medicine.iupui.edu/clinpharm/ddis/table.aspx>. The general categorization into strong, moderate, and weak inhibitors according to the website is displayed below. Refer to [Section 6.1.2.1](#) on instructions for concomitant use of CYP3A inhibitors or inducers with ibrutinib.

Inhibitors of CYP3A	Inducers of CYP3A
Strong inhibitors:	Carbamazepine
INDINAVIR	Efavirenz
NELFINAVIR	Nevirapine
RITONAVIR	Barbiturates
CLARITHROMYCIN	Glucocorticoids
ITRACONAZOLE	Modafinil
KETOCONAZOLE	Oxcarbazepine
NEFAZODONE	Phenobarbital
SAQUINAVIR	Phenytoin
SUBOXONE	Pioglitazone
TELITHROMYCIN	Rifabutin
Moderate inhibitors:	Rifampin
Aprepitant	St. John's Wort
Erythromycin	Troglitazone
diltiazem	
Fluconazole	
grapefruit juice	
Seville orange juice	
Verapamil	
Weak inhibitors:	
Cimetidine	
All other inhibitors:	
Amiodarone	
NOT azithromycin	
Chloramphenicol	
Boceprevir	
Ciprofloxacin	
Delaviridine	
diethyl-dithiocarbamate	
Fluvoxamine	
Gestodene	
Imatinib	
Mibefradil	
Mifepristone	
Norfloxacin	
Norfluoxetine	
star fruit	
Telaprevir	
Troleandomycin	
Voriconazole	

Source: <http://medicine.iupui.edu/clinpharm/ddis/table.aspx>.

Appendix 4. Modified 6th WM Response Criteria (NCCN 2014) for Investigator Assessment

Modified WM Response Criteria for Investigator Assessment of Response and Progression*	
Category	Response Criteria
Complete Response (CR)	
 • Serum IgM values in normal range • Disappearance of monoclonal protein by immunofixation Note: Reconfirmation of CR status is required with a second immunofixation at any time point • No histological evidence of bone marrow involvement • Complete resolution of lymphadenopathy⁴/splenomegaly if present at baseline
Very Good Partial Response (VGPR)	
 • At least 90% reduction of serum IgM from baseline or serum IgM values in normal range • Reduction in lymphadenopathy⁴/splenomegaly if present at baseline
Partial Response (PR)	
 • At least 50% reduction of serum IgM from baseline • Reduction in lymphadenopathy⁴/splenomegaly if present at baseline
Minor Response (MR)	
 • At least 25% but <50% reduction of serum IgM from baseline
Stable Disease (SD)	
 • Not meeting criteria for CR, VGPR, PR, MR, or progressive disease (PD)
Progressive Disease (PD)	
At least one of the following
 
 • A $\geq 25\%$ increase in serum IgM with a total increase of at least 500 mg/dL from nadir¹ 
 ○ Confirmation of the initial IgM increase is required when IgM is sole criterion for progressive disease. • Appearance of a new lymph nodes > 1.5 cm in any axis, $\geq 50\%$ increase from nadir in sum of product of diameters (SPD) of more than one node, or $\geq 50\%$ increase in longest diameter of a previously identified node > 1 cm in short axis² • Appearance of new splenomegaly or $\geq 50\%$ increase from nadir in enlargement of the spleen² • Appearance of new extranodal disease^{2/3} • New or recurrent involvement in the bone marrow • New symptomatic disease on the basis of malignant pleural effusion, Bing Neel (WM CNS disease) syndrome, amyloidosis or light chain deposition disease, or other paraprotein mediated disorder.

1. Nadir for serum IgM is defined as the lowest serum IgM value obtained at any time from baseline onwards with the exception that serum IgM levels post-plasmapheresis will not be considered for up to 35 days.
2. For additional clarification to assess the appearance or progression of existing nodal and extranodal disease (Refer to [Section 7.5.4.](#))
3. Measurable extranodal disease should be assessed in a manner similar to that for nodal disease.
4. Sum of the products of multiple lymph nodes (as evaluated by CT scans) or the longest diameter of one target lymph node

* The primary efficacy evaluations are based on IRC evaluation. In addition, eligibility for potential next-line therapy with ibrutinib will be based on IRC confirmed progression. The IRC assessment will incorporate assessments from the central radiology review and the details regarding the IRC evaluation for response and progression will be outlined in a separate charter.

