4.1.2. Exclusion Criteria

Any potential subject who meets any of the following criteria will be excluded from participating in the study.

1. Known involvement of the central nervous system by WM.
2. Disease that is refractory to the last prior rituximab-containing therapy defined as either
 - Relapse after the last rituximab-containing therapy <12 months since last dose of rituximab,

OR

- Failure to achieve at least a MR after the last rituximab-containing therapy.

If the subject meets this exclusion criterion and therefore is excluded from the main randomized study, participation in the non randomized substudy (Arm C) may be considered ([Section 4.2](#))

3. Rituximab treatment within the last 12 months before the first dose of study drug.
4. Known anaphylaxis or IgE-mediated hypersensitivity to murine proteins or to any component of rituximab.
5. Prior exposure to ibrutinib or other BTK inhibitors.
6. Received any WM-related therapy (eg, chemotherapy, immunotherapy, investigational drug) ≤30 days prior to first administration of study treatment.
7. Plasmapheresis <35 days prior to the initiation of study drug, except when at least one serum IgM central assessment was performed during the screening period and was >35 days from the most recent plasmapheresis procedure.
 - Subjects with high IgM values or viscosity symptoms during screening may receive plasmapheresis prior to initiating study drug (refer to [Section 6.3](#)) if the previous plasmapheresis was performed >35 days before the plasmapheresis performed during screening (in order to obtain a true baseline IgM value for efficacy evaluations).
8. History of other malignancies, except:
 - Malignancy treated with curative intent and with no known active disease present for ≥3 years before the first dose of study drug and felt to be at low risk for recurrence by treating physician.
 - Adequately treated non-melanoma skin cancer or lentigo maligna without evidence of disease.
 - Adequately treated carcinoma in situ without evidence of disease.
9. Vaccinated with live, attenuated vaccines within 4 weeks of first dose of study drug.
10. Recent infection requiring systemic treatment that was completed ≤14 days before the first dose of study drug.
11. Known bleeding disorders (eg, von Willebrand's disease) or hemophilia.

12. History of stroke or intracranial hemorrhage within 12 months prior to enrollment.
13. Known history of infection with human immunodeficiency virus (HIV).

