10.6.3.4. Clinical Response Rate

Clinical Response Rate (CRR) is defined as the proportion of subjects who achieve MR or better according to the modified IVth IWWM (NCCN 2014) criteria as assessed by the IRC. CRR will be analyzed in a similar fashion as ORR.

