CRR by IRC, CRR by investigator	Proportion of subjects achieving a best overall response of confirmed CR, VGPR, PR or MR at or prior to initiation of subsequent antineoplastic therapy.	Same analyses as for ORR	

PCYC-1127-CA Statistical Analysis Plan

Page 16 of 18

Endpoint	Definition	Analysis Methods	
IgM, Hgb	Value and change from baseline	Descriptive summary statistics	
Lymph nodes and spleen	Sum of product of diameters for target nodal lesions, spleen depth and spleen volume	Descriptive summary statistics	
Tumor involvement of bone marrow	Cellularity and intertrabecular space	Descriptive summary statistics	
Medical resource utilization	Number of plasmapheresis, number of emergency room visits, number and days of hospitalizations	Descriptive summary statistics	
EQ-5D-5L visual analog scale and utility score, FACT-An total score and subscale scores	Value and change from baseline, proportion of subjects achieving clinically meaningful improvement, time to improvement. Clinically meaningful improvement is defined as an increase of \geq 7 points for visual analog scale (or \geq 0.08 points for utility score, \geq 7 points for FACT-An total score, \geq 6 points for anemia subscale score, \geq 3 points for fatigue subscale score) prior to initiation of subsequent antineoplastic therapy.	Descriptive summary statistics. The proportion of subjects achieving clinically meaningful improvement will be compared between the two randomized treatment arms using chi-square test. 95% CI for the rate ratio will be calculated. For each parameter, change from baseline up to Week 49 will be analyzed using the Mixed-Effects Model Repeated Measure (MMRM). The model includes the baseline scores, baseline ECOG (0, 1-2), prior treatment history on CRF (previously untreated, previously treated), WM IPSS on CRF (low, intermediate, high) as covariates; treatment, time point and treatment-by-time point interaction as fixed effects; and subjects as random effect. An unstructured (co)variance structure will be used to model the within-subject error. Kenward-Roger's approximation will be used to estimate denominator degrees of freedom. The 2-sided 95% CIs will be calculated	

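### Appendix 4 ranks an IgM fall of 50% or more without nodal or splenic reduction below a 25% to <50% fall, so some subjects can be miscounted as non-responders in the exploratory clinical response rate

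*Protocol*

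**What the plan says.** Protocol Appendix 4 sets the response classes.

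- **MR** depends on IgM alone: "At least 25% but <50% reduction of serum IgM from baseline".
- **Partial response (PR)** has two parts: "At least 50% reduction of serum IgM from baseline" and "Reduction in lymphadenopathy⁴/splenomegaly if present at baseline".
- **Very good partial response (VGPR)** has the same nodal and splenic condition with a stricter IgM requirement (a 90% fall or a normal value).
- **Complete response (CR)** asks, among other things, for "Complete resolution of lymphadenopathy⁴/splenomegaly if present at baseline".
- **SD** is the residual class: "Not meeting criteria for CR, VGPR, PR, MR, or progressive disease (PD".

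Protocol Section 10.6.3.4 states: "Clinical Response Rate (CRR) is defined as the proportion of subjects who achieve MR or better". SAP Section 4.1, Table 2, gives the working definition, for IRC and for investigator: "Proportion of subjects achieving a best overall response of confirmed CR, VGPR, PR or MR at or prior to initiation of subsequent antineoplastic therapy". CRR is listed there as exploratory and is analysed in the same way as ORR.

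The Appendix 4 table is headed for investigator assessment. Its footnote and Protocol Section 10.10 leave the IRC rules to a separate charter, which is not among the documents. Protocol Section 7.5 nevertheless cites Appendix 4 for response assessments in general.

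**The concern.** An ordered response scale should not drop a subject to a lower class because the marker improved. Here MR has an upper limit on the IgM fall, while the next class up adds a second condition. A subject who passes the limit but fails the second condition belongs to neither class, and the residual rule makes that subject SD. I found no other section that reassigns this combination.

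The boundary between SD and MR decides who counts in CRR. If the combination persists, a subject with a deep IgM fall can be recorded as a non-responder while a subject with a smaller fall counts as a responder.

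**Working it through.** The plan states no figure on this point, so there is none to reproduce. The check applies the Appendix 4 rules as written and then follows them into best overall response.

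**1. Class at a single assessment** (no CR, no PD, IgM not in the normal range)

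| IgM fall from baseline | No baseline nodes/spleen, or reduced | Present at baseline, not reduced |
|---|---|---|
| 20% | SD | SD |
| 25%, 40%, 49% | MR | MR |
| 50%, 60%, 80% | PR | **SD** |
| 90%, 95% | VGPR | **SD** |

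The middle column is ordered. The right-hand column rises to MR and falls back to SD at 50%.

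**2. From one assessment to CRR.** The SAP counts best overall response up to subsequent therapy. A subject in the bold cells is still a CRR responder if any assessment fell between 25% and <50%, or if a later scan shows reduction. Inputs from the Protocol:

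- Overall disease assessment starts at Week 5 and runs every 4 weeks to Week 16 (Section 8.3.3, Appendix 1).
- The Week 2 to 4 immunoglobulin values are labelled as safety observations for IgM flare (Appendix 1, footnote j).
- Follow-up CT is at Weeks 17, 33, 49, 65, 81 and 97, then every 24 weeks, for subjects with nodal or extranodal disease at Screening.

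**3. Which IgM courses miss the MR band?** Assume, for illustration, that nodes never shrink and that the IgM fall approaches 70% exponentially with half-time h weeks:

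fall at Week w = 0.70 × (1 − 2^(−(w−1)/h))

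Assessments at Weeks 5, 9, 13, 17, 21, 25, 33, 41 and 49 give:

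| h (weeks) | Week 5 | Week 9 | Week 13 | Visits in MR band | Best response |
|---|---|---|---|---|---|
| 1 | 0.66 | 0.70 | 0.70 | 0 | SD |
| 2 | 0.52 | 0.66 | 0.69 | 0 | SD |
| 3 | 0.42 | 0.59 | 0.66 | 1 | MR |
| 4 | 0.35 | 0.52 | 0.61 | 1 | MR |
| 6 | 0.26 | 0.42 | 0.52 | 2 | MR |
| 8 | 0.21 | 0.35 | 0.45 | 2 | MR |
| 12 | 0.14 | 0.26 | 0.35 | 4 | MR |

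Under this assumption the band is missed when 2^(−4/h) ≤ 1 − 0.50/0.70 = 0.286, that is h ≤ 4/log2(3.5) = 4/1.807 = 2.2 weeks.

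The MR results assume that one visit is enough. The SAP wording speaks of confirmed responses, but the documents define confirmation only for CR (a second immunofixation in Appendix 4). If MR needed two assessments, half-times of 3 and 4 weeks would also end as SD.

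**4. Size.** The documents do not give the share of subjects with this pattern throughout. As a conversion only, assumed shares of 0%, 2%, 5% and 10% of a 75-subject arm are 0, 1.5, 3.75 and 7.5 subjects, and the same number of percentage points of CRR in that arm.

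**5. Effect of closing the gap.** If MR had no upper limit but excluded PR or better and PD, the bold cells would become MR. CRR could only rise. ORR and duration of response start at PR, and PFS depends on PD and death, so none of them moves.

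**The case against.** The strongest reply is that best overall response removes most of the problem. This stands in large part. PR asks for a reduction with no percentage threshold, so a later scan showing even modest shrinkage makes the subject a PR. A provisional SD label before the Week 17 CT is overridden in the same way. Early IgM flare, which Protocol Section 6.3 says occurs in up to 50% of patients on rituximab, also makes a fall beyond 50% by Week 5 less likely in Arms A and B. On the other side, Protocol Section 1.6.2 reports a median time to response of 4 weeks on ibrutinib alone, so a fast course cannot be excluded.

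It can also be said that CRR is exploratory and outside the testing order in SAP Section 1.6, and that the table adapts a consensus system. Both are correct. They limit the importance of the gap but do not close it.

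A reader might infer three stronger points, which the documents do not support:

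- **IRC-assessed CRR is understated.** The IRC rules are in a charter that is not available and may already deal with this combination. The general reference in Section 7.5 justifies a check, not a conclusion.
- **The comparison between arms is distorted.** The pattern needs a deep IgM fall together with nodes that do not shrink. Better IgM response in Arm A does not imply more of these discordant cases, because nodes may shrink more often there too. If they were commoner in Arm A, the error would count against ibrutinib.
- **Subjects are wrongly sent to Arm C.** The exclusion reads "Failure to achieve at least a MR after the last rituximab-containing therapy". It does not cite Appendix 4, and its natural meaning includes deeper responses. Section 3.1 ties relapsed or refractory status to the modified criteria, but nothing tells sites to re-derive past responses from this table; Section 7.1.3 takes them from records and interview. Arm C is only something that may be considered.

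**Conclusion.** The gap is real on the text. With baseline lymphadenopathy or splenomegaly not reduced and no PD, the class falls from MR to SD once the IgM reduction reaches 50%.

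The consequence is narrow. A subject is miscounted in CRR only if both of these hold:

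- no assessment yields a countable MR, because IgM has passed the band before Week 5 or because the MR is not confirmed, a term left undefined for MR;
- no reduction of nodes or spleen is shown before subsequent therapy.

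This applies directly to investigator CRR, and to IRC CRR only if the charter uses the same table. It would be wrong to say that every such subject is lost. The documents give neither the number affected nor any between-arm effect; the IgM courses and the 0% to 10% shares above are assumptions. The primary endpoint, ORR and duration of response are unaffected. The point is a defect in an exploratory endpoint that is worth correcting because correction is cheap.

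**What to change.** In Appendix 4 and in the SAP derivation of CRR, define MR as at least a 25% reduction in IgM from baseline that does not meet PR, VGPR, CR or PD. State whether MR needs confirmation and, if so, by what. Check the IRC charter for the same combination and align it if needed.

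The cost is one line of derivation on data already collected. The downside is a small departure from the adapted consensus wording, so CRR under the literal wording can be shown beside it as a sensitivity result. The difference between the two then gives the number affected in each arm. If results by arm have already been seen, label the revised CRR as a post hoc clarification.

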Appendix 5. New York Heart Association Functional Classification

NYHA Class Symptoms	NYHA Class Symptoms
I	No symptoms and no limitation in ordinary physical activity, eg, shortness of breath when walking, climbing stairs etc.
II	Mild symptoms (mild shortness of breath and/or angina) and slight limitation during ordinary activity.
III	Marked limitation in activity due to symptoms, even during less-than-ordinary activity, eg, walking short distances (20–100 m). Comfortable only at rest.
IV	Severe limitations. Experiences symptoms even while at rest. Mostly bedbound patients.

Appendix 6. WM IPSS Calculation

Factors associated with Prognosis	Value
Age	> 65 years
Hemoglobin	≤ 11.5 g/dL
Platelet count	≤ 100 x 10 ⁹ /L
β ₂ -microglobulin	> 3 mg/L
Serum monoclonal IgM	> 7.0 g/dL
Risk Category	Score
I (low risk)	0 or 1 factors (≤ 65 years)
II (intermediate risk)	2 factors OR age > 65 years
III (high risk)	> 2 factors

An international prognostic scoring system for newly diagnosed WM patients was recently developed ([Morel et al, 2009](#)) based on 5 factors associated with a poor prognosis include advanced age, high beta 2-microglobulin (β₂M), low albumin, cytopenias, serum IgM monoclonal protein, and organomegaly

Appendix 7. EQ-5D-5L Health Questionnaire

Health Questionnaire

English version for the UK

SAMPLE

UK (English) v.2 © 2009 EuroQol Group. EQ-5D™ is a trade mark of the EuroQol Group

Under each heading, please tick the ONE box that best describes your health TODAY

MOBILITY

- I have no problems in walking about
- I have slight problems in walking about
- I have moderate problems in walking about
- I have severe problems in walking about
- I am unable to walk about

SELF-CARE

- I have no problems washing or dressing myself
- I have slight problems washing or dressing myself
- I have moderate problems washing or dressing myself
- I have severe problems washing or dressing myself
- I am unable to wash or dress myself

USUAL ACTIVITIES (e.g. work, study, housework, family or leisure activities)

- I have no problems doing my usual activities
- I have slight problems doing my usual activities
- I have moderate problems doing my usual activities
- I have severe problems doing my usual activities
- I am unable to do my usual activities

PAIN / DISCOMFORT

- I have no pain or discomfort
- I have slight pain or discomfort
- I have moderate pain or discomfort
- I have severe pain or discomfort
- I have extreme pain or discomfort

ANXIETY / DEPRESSION

[figure not shown]
- I am not anxious or depressed
- I am slightly anxious or depressed
- I am moderately anxious or depressed
- I am severely anxious or depressed
- I am extremely anxious or depressed

- We would like to know how good or bad your health is TODAY.
- This scale is numbered from 0 to 100.
- 100 means the best health you can imagine.
0 means the worst health you can imagine.
- Mark an X on the scale to indicate how your health is TODAY.
- Now, please write the number you marked on the scale in the box below.

YOUR HEALTH TODAY =

SAMPLE

The best health
you can imagine

The worst health
you can imagine

Appendix 8. FACT-An (Version 4)

Below is a list of statements that other people with your illness have said are important. **Please circle or mark one number per line to indicate your response as it applies to the past 7 days.**

PHYSICAL WELL-BEING		Not at all	A little bit	Some what	Quite a bit	Very much
GP1	I have a lack of energy	0	1	2	3	4
GP2	I have nausea	0	1	2	3	4
GP3	Because of my physical condition, I have trouble meeting the needs of my family	0	1	2	3	4
GP4	I have pain.....	0	1	2	3	4
GP5	I am bothered by side effects of treatment.....	0	1	2	3	4
GP6	I feel ill.....	0	1	2	3	4
GP7	I am forced to spend time in bed.....	0	1	2	3	4

SOCIAL/FAMILY WELL-BEING		Not at all	A little bit	Some what	Quite a bit	Very much
GS1	I feel close to my friends.....	0	1	2	3	4
GS2	I get emotional support from my family	0	1	2	3	4
GS3	I get support from my friends	0	1	2	3	4
GS4	My family has accepted my illness	0	1	2	3	4
GS5	I am satisfied with family communication about my illness	0	1	2	3	4
GS6	I feel close to my partner (or the person who is my main support)	0	1	2	3	4
Q1	Regardless of your current level of sexual activity, please answer the following question. If you prefer not to answer it, please mark this box  and go to the next section.					
GS7	I am satisfied with my sex life	0	1	2	3	4

Please circle or mark one number per line to indicate your response as it applies to the past 7 days.

EMOTIONAL WELL-BEING		Not at all	A little bit	Some what	Quite a bit	Very much
GE1	I feel sad.....	0	1	2	3	4
GE2	I am satisfied with how I am coping with my illness	0	1	2	3	4
GE3	I am losing hope in the fight against my illness.....	0	1	2	3	4
GE4	I feel nervous.....	0	1	2	3	4
GE5	I worry about dying.....	0	1	2	3	4
GE6	I worry that my condition will get worse.....	0	1	2	3	4

FUNCTIONAL WELL-BEING		Not at all	A little bit	Some what	Quite a bit	Very much
GF1	I am able to work (include work at home).....	0	1	2	3	4
GF2	My work (include work at home) is fulfilling	0	1	2	3	4
GF3	I am able to enjoy life	0	1	2	3	4
GF4	I have accepted my illness	0	1	2	3	4
GF5	I am sleeping well	0	1	2	3	4
GF6	I am enjoying the things I usually do for fun.....	0	1	2	3	4
GF7	I am content with the quality of my life right now .	0	1	2	3	4

Please circle or mark one number per line to indicate your response as it applies to the past 7 days.

ADDITIONAL CONCERNS		Not at all	A little bit	Some what	Quite a bit	Very much
HI7	I feel fatigued	0	1	2	3	4
HI12	I feel weak all over.....	0	1	2	3	4
An1	I feel listless (“washed out”).....	0	1	2	3	4
An2	I feel tired.....	0	1	2	3	4
An3	I have trouble starting things because I am tired	0	1	2	3	4
An4	I have trouble finishing things because I am tired ..	0	1	2	3	4
An5	I have energy	0	1	2	3	4
An6	I have trouble walking	0	1	2	3	4
An7	I am able to do my usual activities	0	1	2	3	4
An8	I need to sleep during the day	0	1	2	3	4
An9	I feel lightheaded (dizzy)	0	1	2	3	4
An10	I get headaches.....	0	1	2	3	4
B1	I have been short of breath.....	0	1	2	3	4
An11	I have pain in my chest	0	1	2	3	4
An12	I am too tired to eat	0	1	2	3	4
BL4	I am interested in sex	0	1	2	3	4
An13	I am motivated to do my usual activities	0	1	2	3	4
An14	I need help doing my usual activities.....	0	1	2	3	4
An15	I am frustrated by being too tired to do the things I want to do	0	1	2	3	4
An16	I have to limit my social activity because I am tired	0	1	2	3	4

Appendix 9. Schedule of Assessments for Subjects Treated with Placebo in Combination with Rituximab and Documented IRC confirmed Progression who Elect to Receive Next-line Ibrutinib Therapy

Study Weeks	Assessment for Eligibility for Next-line Ibrutinib Therapy	Treatment Phase			Follow-up Phase
		Every 4 weeks for 16 weeks	Every 8 weeks thereafter until PD	End-of-Treatment Visit	Follow-up (Every 12 weeks)
Study Windows		±3 d	±3 d	30 (±3 d)	±7 d
Study Drug Administration					
Ibrutinib 420 mg per day PO		Continuous Daily Dosing			
Procedures					
IRC-confirmed PD ^a	x				
Sponsor's Designee approval	x				
Concomitant medications	x	x	x	x	
Adverse events		x	x	x	
Physical examination, vital signs, ECOG	x ^b	x	x	x	
Hematology ^c	x ^b	x	x	x	
Serum chemistry ^c	x ^b	x	x	x	
Serum immunoglobulins ^c (IgM)	x ^b	x	x	x	
Investigator assessment of response and for progression		x	x		
Survival status					x
Subsequent anticancer therapies					x

d=day; ECOG=Eastern Cooperative Oncology Group; IRC=Independent Review Committee; PD=progressive disease; PO=oral; qd=once daily

^a Documentation from IRC required for Sponsor's designee approval to receive next-line ibrutinib therapy

^b Assessments for next-line ibrutinib should be performed ±10 days from unblinding

^c Assessments performed by local laboratory

